5.5.6 Vital Signs

The following summaries will be produced for all vital sign's parameters:

- Shift tables of low, normal, high distribution (n; %) at each post-baseline cycle by baseline (cycle 1 day 1) distribution.

5.5.7 Physical Examination

The following summaries will be produced for all physical examination's parameters:

- Shift tables of low, normal, high distribution (n; %) at each post-baseline cycle by baseline (cycle 1 day 1) distribution.

5.6 Interim Analysis of Safety

No interim analysis is planned.

5.7 Changes of Analysis from Protocol

- The level of significance α has been changed from \leq to $=$ in some paragraphs.
- We have included the time to response as secondary endpoint. We have dropped the time to progression.

5.8 Deviations from SAP

Any deviations from the original statistical plan will be described and justified in the final clinical study report.

6 APPENDICES

6.1 Appendix 1 - SAS Codes

All report outputs will be produced using SAS® version 9.4 (TS1M5) version in a secure and validated environment.

ORR will be estimated with the 95% Clopper-Pearson confidence intervals and the P-value with exact binomial test.

```
proc freq data=FAS;
  tables ORR / binomial(exact p=.05) alpha=.05;
  title 'ORR (FAS)';
run;
```

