1.6 Sample Size

A total of 18 patients will be enrolled and the defined primary endpoint is ORR.

Justification of Sample Size:

The sample size calculation is based on an exact binomial test. The clinical trial is designed to demonstrate an ORR of at least 25% and to exclude a rate of less than 5% ($p_0=0.05$, $p_1=0.25$, $\alpha =0.05$, $\beta=0.80$, A'herne's exact design). At least 3 responders (18.8%) among 16 evaluable patients will be adequate to justify the investigation of this strategy in further clinical trials. Considering a drop-out rate of 10%, a sample size of 18 patients will be needed to attain 80% power at nominal level of one-sided alpha of 0.05.

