4 ANALYSIS SETS

The following sets will be analyzed:

- **Screening:** Patients who were present at the screening visit.
- **Safety and FAS (Full Analysis Set) Set:** patients who receive at least one dose of study medication.

Efficacy and Safety endpoints will be analyzed on the Safety/FAS set.

FAS set will be considered the primary population for the analysis.

- **Per-protocol (PP) set:** All patients that accomplish selection criteria, receive at least one drug exposure, and receive the protocol required study drug exposure and processing. Criteria for determining the “per protocol” (PP) group assignment would be established by the Steering Committee before the statistical analysis begins. This analysis will only occur if this set differs by $\geq 10\%$ from the FAS set.

The primary and secondary efficacy analyses will be performed on the FAS and PP sets.

- **Exploratory Set:** All patients with biomarker evaluable samples with the assay and alternative platforms that accomplish selection criteria and receive at least one drug exposure.

Exploratory analysis will be performed on exploratory set. A separate analysis report for such assessments will be written.

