5.4.3 Decision Rules and Adjustment of Alpha for Primary Endpoint

The study would be defined as positive at final analysis, if the ORR in the INCMGA00012 arm is statistically significantly better ($p<0.05$) than expected under the null hypothesis ($H_0: ORR \leq 5\%$). Decisions will be based on exact binomial test.

For all secondary and exploratory tests, we will use two-sided P-values with alpha=0.05 level of significance. The P-values emerging from these analyses will not be interpreted in a confirmative sense; they will be considered of descriptive nature only.

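### The SAP text requires an exact binomial p-value for the primary test, but the printed SAS program has no statement requesting one; if it prints the asymptotic test instead, the two disagree at 3 responders of 17 or 18

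*SAP*

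**What the plan says.** SAP 5.4.3 calls the study positive if ORR is significantly better (p<0.05) than under H0: ORR ≤ 5%, and adds: "Decisions will be based on exact binomial test". Protocol 8.4.5 has the same rule. SAP 5.4.2 and the sentence directly above the program in Appendix 6.1 both promise a Clopper-Pearson interval and an exact binomial p-value. SAP 1.6 gives the side: 18 patients for "80% power at nominal level of one-sided alpha of 0.05".

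The program in Appendix 6.1 is PROC FREQ on the FAS with one TABLES statement, "tables ORR / binomial(exact p=.05) alpha=.05", followed by a title and `run`. It contains no separate `EXACT` statement and no `LEVEL=` option. It is the only code the SAP gives for the primary endpoint.

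On the denominator, SAP section 4 defines the FAS as everyone who received at least one dose, and says "FAS set will be considered the primary population for the analysis". SAP Table 1 counts patients without a post-baseline assessment as non-responders. The primary denominator can therefore be as large as 18.

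**The concern.** The text and the code of one prespecified plan appear to ask for different tests. The word `exact` sits inside the parentheses of the BINOMIAL option. In standard PROC FREQ behaviour that placement requests exact confidence limits, while the test against `p=.05` stays a normal-approximation z-test unless a separate `EXACT BINOMIAL` statement is given. The documents say nothing about the software, so this is an assumption.

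If it holds, the program prints a p-value that is not the one in the decision rule. With so few patients and a null rate of 5%, the two p-values can fall on opposite sides of 0.05. The count where this happens is 3, the number of responders that SAP 1.6 names as adequate. Someone would then have to choose between text and code after seeing the data.

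**Working it through.** **Inputs.** p0 = 0.05, p1 = 0.25, one-sided alpha 0.05, power 80%, 3 of 16 evaluable, 10% drop-out and N = 18 come from SAP 1.6. H0: ORR ≤ 5% and p<0.05 come from SAP 5.4.3. The FAS denominator comes from SAP section 4 and Table 1.

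**The plan's own figure.** The exact one-sided tail at p0 is P(X ≥ 3 | n = 16) = 1 − (0.4401 + 0.3706 + 0.1463) = 0.0429. At p1 the same tail is 0.803. No smaller n meets both the 5% and the 80% limits, and 16/0.9 = 17.8 rounds up to 18. The design reproduces.

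**Formulas for the analysis.**
- Exact one-sided p: P(X ≥ x | n, 0.05).
- Asymptotic test: z = (x/n − 0.05)/√(0.05 × 0.95/n), with no continuity correction, since the program requests none.

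**Three of 18.**
- Exact: 1 − (0.3972 + 0.3763 + 0.1683) = 0.058, not below 0.05.
- Asymptotic: z = (0.1667 − 0.05)/0.05137 = 2.271, giving p = 0.012 one-sided or 0.023 two-sided, both below 0.05.

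**Other counts, with responders as the tested level.**

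| Responders/n | Exact one-sided p | Asymptotic one-sided p | Same verdict? |
|---|---|---|---|
| 2/18 | 0.226 | 0.117 | yes, not positive |
| 3/18 | 0.058 | 0.012 | no |
| 4/18 | 0.011 | 0.0004 | yes, positive |
| 3/17 | 0.0503 | 0.008 | no |
| 3/16 | 0.043 | 0.006 | yes, positive |

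The disagreement at 3/18 does not depend on the side. The two-sided exact p is 0.116 by doubling, or 0.058 by summing the outcomes no more likely than the one seen; the asymptotic two-sided p is 0.023.

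**Operating characteristics at n = 18.**
- Asymptotic rule: positive at 3 or more, true size 5.8%, power 86.5% at ORR 25%.
- Exact rule: positive at 4 or more, size 1.1%, power 69.4%.
- Probability of exactly 3 of 18: 17.0% if the true ORR is 25%, and 4.7% if it is 5%.

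**The case against.** The strongest reply is that the text governs. The exact test is named in SAP 5.4.2, in SAP 5.4.3, in the sentence above the code, and in protocol 8.4.5 and 8.4.6. A statistician who follows these would notice a missing exact p-value and add it. The software behaviour is also not in the documents, and the program has not been run for this review. This stands in part: the point is conditional on that behaviour, and it does not show that a wrong result would be reported. It does not remove the conflict, because the appendix belongs to the SAP and is its only program for the deciding p-value.

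It is also fair that the scope is narrow. At the design's n = 16 the two tests agree at 3 responders, and at n = 18 only one count is affected.

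Two stronger readings are tempting, and the documents do not support them.

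- A reader might infer that the program tests non-response and would call an inactive drug significant. The coding of ORR is not given, so this cannot be established, and the output would show which proportion was tested. What stands is that the responder level should be named, because by default (again standard PROC FREQ behaviour) the first level is used.
- A reader might infer that the side of the primary test is undefined, since 5.4.3 does not repeat the word one-sided. But its null is ORR ≤ 5%, it asks for a better rate, its next paragraph applies two-sided p-values to the secondary and exploratory tests, and SAP 1.6 states one-sided alpha. Adding the word is a clarification.

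**Conclusion.** The point holds in conditional form. The SAP requires an exact binomial p-value, and the printed program contains no separate request for one and does not name the responder level. If PROC FREQ behaves as assumed and responders are the tested level, program and decision rule give opposite verdicts at 3 of 18 and at 3 of 17, and agree at 3 of 16. Following the program's p-value at n = 18 would raise the true one-sided size from 1.1% to 5.8%, slightly above the nominal 5%. If a test run shows that the program does print the exact p-value for responders, the disagreement disappears and only the wording needs tidying.

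A reader might also infer that repairing the code restores the design's cut-off. It does not. SAP 1.6 says "At least 3 responders (18.8%) among 16 evaluable patients will be adequate to justify the investigation of this strategy in further clinical trials", whereas the exact test on 18 patients needs 4. That mismatch comes from the denominator, exists whichever program is used, and needs its own resolution.

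**What to change.** Change the SAP only, before the data are analysed.

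- In Appendix 6.1, add the statement `exact binomial;` to the PROC FREQ step.
- In the TABLES statement, set `LEVEL=` inside the BINOMIAL option to the value that codes a responder in the analysis dataset, and state that coding in the SAP.
- Say that the exact one-sided p-value from this output is the one compared with 0.05. Adding one-sided to SAP 5.4.3 brings it into line with SAP 1.6.
- Run the revised program once on a dummy dataset with 3 responders of 18, and check that it prints an exact one-sided p of 0.058 for responders.

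The cost is two edits to the program, a short addition to the text and one test run. Design, data collection and patients are unaffected. Protocol 8.4.5 need not be touched, which avoids the amendment or administrative letter that protocol 12.2 requires for any protocol change.

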6.2 List of Tables, Listings, Figures

A complete list of tables, listings and figures (TLFs) will be given in a separate document which can be updated without updating the SAP. The list will serve as a reference for both the Sponsor, the trial statistician and the statistical programmer and includes the totality of statistical output to be produced.

All output will be headed with an appropriate heading specifying the study ID and abbreviated study title.

All output will be dated and have page numbers in the form 'Page [x / y]' where x denotes the current page within an output and y the total number of pages of that output.

All statistical output will identify the underlying analysis sets and indicate the number of patients/events in this set (N) and the number of patient/events actuals contributing to the output (n). All statistical output will be presented per treatment (if applicable).

All patient listings will contain additionally to the patient identification the analysis set and the treatment.
